8.5 Sample Size and Power Considerations of Primary and Secondary Objectives

Efficacy objectives:

Sample size and power consideration for the aQIV efficacy objective is based on criteria for demonstrating efficacy in placebo controlled studies provided in CBER guidance, specifically that the study should be powered to assess the lower bound of the two-sided 95% CI of vaccine effectiveness, anticipated to be substantially above zero. This study is planned using a group sequential design. The power of Cox Regression which is planned to be used for analysis is dependent on the overall number of influenza cases, so the sample sizes on number of subjects described in this section is provided more for operational reasons. Additional information on the planning of number of subjects that may need to be enroled if it is decided to continue enrolment after interim analyses is described in [Section 8.6](#).

For the primary efficacy objective: with 1-sided alpha of 2.5% and assuming an attack rate of influenza of 3.5% among subjects enroled in the non-influenza comparator group and 1.4% among the aQIV group, i.e. 60% assumed vaccine efficacy for aQIV, 238 events (i.e. 4,860 subjects per group under the assumed ERs) are needed with 86.5% power to show the absolute efficacy of aQIV versus non-influenza comparator, in preventing first occurrence RT-PCR-confirmed influenza A and/or B, due to any strain of influenza regardless of antigenic match to the strains in aQIV, in subjects ≥ 65 years of age, using a margin of 40% for lower bound of the CI for absolute vaccine efficacy.

For the first secondary efficacy objective: with a group vaccine efficacy of 65% but expecting conservatively reduced event rates of influenza cases due to matched strains of 2.5% among subjects in the non-influenza comparator group and 0.9% among the aQIV group then 144 events has estimated power approximately 88.5% to show the absolute efficacy of aQIV versus non-influenza comparator, using a margin of 40% for lower bound of the CI.

Assuming a drop-out rate of 10%, approximately 10,692 subjects \geq 65 years, 5,346 per vaccine group will be randomized to receive either aQIV or non-influenza comparator (Boostrix®) in a 1:1 allocation ratio, stratifying by age (\geq 65 to 74 and \geq 75 years of age), study site and by low vs high risk of influenza complications (score <50 vs \geq 50).

Immunogenicity objective:

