At each interim stage, α -boundaries, forming the adjusted probabilities for the type 1 error, are calculated using error-spending function and if the p-value for the test of primary objective is lower than the respective α -boundary the trial stops for efficacy at this stage. Using the same error-spending-function applied on the overall type 2 error of 0.1 (Power 90%), β -boundaries are calculated, i.e. the adjusted probabilities for the type 2 error β , and if the p-value is higher than the β -boundaries, the trial stops early for futility at this stage.

In other words the trial stops early for efficacy if data collected at this stage allows to demonstrate primary efficacy objective (reject null-hypothesis); and the trial stops early for futility, if the data provides sufficient evidence that the test vaccine is not good as expected (the alternative hypotheses of absolute vaccine efficacy over the protocol-specified margin is not true, i.e $VE < 0.4$). Otherwise, the trial continues to the next stage and more subjects will be enrolled.

The cumulative O'Brien-Fleming type error-spending-function (Lan and DeMets, 1983; option ERRFUNCBOF in SAS® PROC SEQDESIGN) will be used for both α - and β -boundaries; the error-spending function is defined as:

$$E(t; \alpha) = \begin{cases} 1 & \text{if } t \geq 1 \\ \frac{1}{\alpha} 2 \left(1 - \Phi\left(\frac{z(1-\alpha/2)}{\sqrt{t}}\right)\right) & \text{if } 0 < t < 1 \\ 0 & \text{otherwise} \end{cases}$$

where α equals α for α spending function and β for beta spending function, and where t is the information fraction.

With a specified type 1 error, α , and information level t at stage k , the cumulative error is $\alpha E(t; \alpha)$ <https://support.sas.com/documentation/onlinedoc/stat/131/seqdesign.pdf>

If the trial proceeds to the final analysis, the boundary for rejection of null hypothesis is identical to the type 1 error (that is as the 0.025 one-sided alpha level) with power specified for the overall design, and the trial stops to either reject or not reject the null hypothesis of the primary objective.

Additional interim analyses may be requested by the DMC, particularly if the first interim analysis is conducted soon after 119 cases of influenza have been reported. In this case, the DMC may request that a second interim analysis be conducted to allow for greater accuracy to determine if the trial should stop or continue.

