Table 8.6-1 shows the needed total number of cases at each stage of the two-stage design together with boundaries for early stopping for futility or efficacy, calculated on p-value scale using the cumulative error spending function. With 1/2 information collected at the stage of interim analysis (that is, with exactly 119 confirmed ILIs) the trial would stop early for futility at this stage in case a p-value higher than 0.35022 is observed, or it would stop early for efficacy if the p-value is lower than 0.00625. Otherwise the trial will be continued and more subjects will be enrolled. The actual boundaries used for decision making would depend on number of confirmed ILIs occurring and reported for Interim Analysis.

Table 8.6-1: Example of a Two Stages Group-Sequential Design

	Stage 1 First Interim	Stage 2 Final
Number of Events	119	238
Alpha Boundary on p-value scale (equivalent to Type 1 error, 1-sided), early stopping for efficacy	0.00625	0.02275
Beta Boundary on p-value scale (equivalent to Type 2 error, 1-sided), early stopping for futility	0.35022	0.02275

The stopping rules given above are statistical and should be completed with clinical and strategic stopping rules that allow the DMC to make a decision on a broader picture of the data which includes safety endpoints and the other endpoints of the study. Another interim look at the data with appropriate adjustment of type 1 error might be recommended before reaching the targeted 238 cases.

Further details of the statistical methods are provided in the SAP and more information regarding clinical or strategic stopping rules will be provided in the DMC charter.

For the interim analyses, if needed a restricted unblinding will be done, i.e. only independent DMC members and unblinded individuals responsible for the analyses will receive access to the randomization codes and unblinded data for the purpose of preparing the interim analyses (further information on handling of the blinding for the interim analyses can be found in [Section 3.3](#)). The results of the interim analyses will be used only for DMC purposes and will not be reported in a Clinical Study Report (CSR).

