12. EFFICACY ANALYSIS

12.1 Primary Objectives Analysis

The primary absolute efficacy objective will be evaluated using following null (H_0) and alternative (H_1) hypotheses:

$$H_0: 1 - HR = VE \leq 0.4 \quad \text{versus} \quad H_1: 1 - HR = VE > 0.4,$$

where HR is a hazard ratio of aQIV versus non-influenza comparator and VE is vaccine efficacy. The primary objective will be demonstrated if the lower limit of the two-sided confidence interval of VE estimate, with at least 95% coverage in a multiple sequential hypothesis testing, exceeds 40%. In case an interim analysis is performed, the 95% CI will be adjusted accordingly. If an interim analysis is performed and the trial doesn't stop, then all the subsequent analysis will be tested at a reduced alpha level, i.e. what's left from the interim analysis. The confidence interval will be higher than 95% instead of 95% for the final analysis.

Primary vaccine efficacy analyses will be based on the Efficacy FAS, and repeated on the Efficacy PPS.

The HR and the related 95% CI of HR, for onset of first RT-PCR confirmed influenza will be estimated by a proportional hazards regression model with treatment effect as a fixed effect and stratifying covariates as a random effect:

$h_i(t|X) = h_0(t) \exp(\beta^T X + b^T Z)$, with t denoting time to the influenza, β is the effect of treatment group indicated by X , b is random effect (assumed as a multivariable random gaussian variable with zero mean and diagonal covariance matrix), Z is random effect covariate (reflecting randomization strata, see [Section 8.1](#) for further discussion of the covariates utilised).

Subjects that did not experience ILI during observation period and subjects that dropped out from the study during observational period will be censored (right-censoring). The estimate of the hazard ratio, the respective estimate for absolute VE and the pertaining 2-sided CIs will be calculated based on this model. If the study continues over several seasons, estimates will be also adjusted for the factor season (s). In case of one or two (interim) analyses, confidence levels at each stage will be adjusted, as discussed in [section 14.1](#), to provide 95% overall coverage.

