- If the number of first-occurrence RT-PCR confirmed influenza cases from 21 through 180 days after vaccination or until the end of the influenza season, whichever is longer, is greater or equal to 120 but less than 238 unblinded interim analyses for efficacy and futility will be performed by the DMC (see below for description).

- If the number of first-occurrence RT-PCR confirmed influenza cases from 21 through 180 days after vaccination or until the end of the influenza season, whichever is longer, is greater or equal to 238 (targeted number of cases to be able to evaluate the primary objective) the trial will be stopped, data will be unblinded and the final analysis will be performed by the Sponsor. If the trial proceeds to the final analysis (upon reaching 238 cases) the boundaries for acceptance or rejection are identical to the assumed type 1 and type 2 errors for the overall design, and the trial stops to either reject or not reject the null hypothesis of the primary objective. That is, the primary objective, i.e. VE against RT-PCR confirmed influenza A and or B will be assess the one-sided 0.025 alpha level.

If the DMC states that the observed data provides already the full information level needed for the final test decision, then the final analysis can be done on full alpha level of one-sided 0.025 and no further enrollment is needed. However if the decision of the group-sequential test is to continue the study then it is on the DMC to determine the number of subjects needed to be additionally enrolled. The DMC should not be influenced by the results of the efficacy testing at the interim analysis when planning further subjects' accrual or the times of future analysis. Only the overall number of cases is allowed to be used for further planning. The following formula for determination of sample sizes for further enrollment may be used:

$$N_{\text{total}} = (C_{\text{planned}} - C_{\text{observed}}) / ER,$$

where N_{total} denotes the total number of subjects needed for further enrollment, C_{planned} is the overall number of cases needed for the test, i.e. 238 cases, C_{observed} is the number of cases observed at current stage, and ER is the observed total attack rate for both groups combined. A drop-out rate of 10% should be added.

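### The stated O'Brien-Fleming-type spending rule with 90% power does not produce the worked-example boundaries, and the final boundary is given as both 0.025 and 0.02275

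*Protocol*

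**What the plan says.** **Spending rule.** Protocol 8.6 states "The cumulative O'Brien-Fleming type error-spending-function" for both boundaries, names the SAS option and prints the formula. SAP 14.1 repeats this. SAP 14.1.1 describes the futility function with the added word *power*.

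**Type II error.** Protocol 8.6: "Using the same error-spending-function applied on the overall type 2 error of 0.1 (Power 90" percent). SAP 14.1 and 14.1.1 also use 0.1. Protocol 8.5 and SAP 5 give a different figure: "238 events (i.e. 4,860 subjects per group under the assumed ERs) are needed with 86.5% power".

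**Worked example.** Protocol Table 8.6-1 and SAP Table 1 are presented as calculated from the spending function with exactly 119 of 238 cases. The trial stops for futility "in case a p-value higher than 0.35022 is observed, or it would stop early for efficacy if the p-value is lower than 0.00625". Both tables give 0.02275 at the final stage. The text adds: "The actual boundaries used for decision making would depend on number of confirmed ILIs".

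**Final boundary.** Protocol 8.6: "the boundary for rejection of null hypothesis is identical to the type 1 error (that is as the 0.025 one-sided alpha level"). SAP 14.1 says the primary objective "will be assess the one-sided 0.025 alpha level". SAP 12.1 says that after an interim that does not stop the trial, "all the subsequent analysis will be tested at a reduced alpha level". The protocol synopsis adjusts the confidence interval for one interim; Protocol 8.2.1.2 mentions adjustment only for more than one.

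**The concern.** The actual limits are to be recomputed from the plan at whatever case count the interim falls on, so the function, the type II error and the final level are the pre-specification. A worked example should confirm that rule. Here it contradicts the rule at a point where the formula can be evaluated directly.

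Two decisions on the primary objective are affected. An interim result can stop the trial under one reading and continue it under the other. A final one-sided p-value between 0.02275 and 0.025 succeeds or fails depending on the passage followed. Any choice made after unblinding could look data-driven.

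**Working it through.** **Inputs.** One-sided alpha 0.025; null HR 0.6 (VE 40%); alternative HR 0.4 (VE 60%); 1:1 allocation; 238 events (Protocol 8.5). Interim at t = 119/238 = 0.5 (Protocol 8.6). Assumption: variance of log HR = 4/D for D events. Final critical values and event numbers were solved by numerical integration of the two-stage normal statistic. *Binding* means the type I error calculation credits the futility stop; *non-binding* means it does not.

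**1. The printed formula at t = 0.5.** Alpha spent = 2 × (1 − Φ(2.2414/√0.5)) = 0.0015, against 0.00625 in the table. Halving the two-sided form of the function gives 0.0028, which does not match either.

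**2. Full designs at t = 0.5.**

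| Spending | Type II error | Futility | Interim efficacy | Interim futility | Final | Events |
|---|---|---|---|---|---|---|
| O'Brien-Fleming type (as stated) | 0.10 | binding | 0.0015 | 0.398 | 0.0253 | 260.0 |
| O'Brien-Fleming type (as stated) | 0.10 | non-binding | 0.0015 | 0.395 | 0.0245 | 262.0 |
| O'Brien-Fleming type | 0.135 | binding | 0.0015 | 0.355 | 0.0256 | 233.4 |
| O'Brien-Fleming type | 0.135 | non-binding | 0.0015 | 0.350 | 0.0245 | 236.2 |
| t² | 0.10 | binding | 0.00625 | 0.35110 | 0.02275 | 267.0 |
| t² | 0.135 | binding | 0.00625 | 0.35022 | 0.02275 | 238.3 |
| **Printed in both tables** | | | **0.00625** | **0.35022** | **0.02275** | **238** |

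Only the t² design with type II error 0.135 and binding futility reproduces the printed line. In particular, 0.025 × 0.5² = 0.00625. At 238 events the printed boundaries have power 86.45%, in line with the stated 86.5%.

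**3. Can 238 events give 90%?** Expected Z at 238 events = ln(0.6/0.4) × √(238/4) = 0.4055 × 7.714 = 3.128. With no interim look, power = Φ(3.128 − 1.960) = 87.9%. A futility look cannot raise this, so no spending function reaches 90% at 238 events on this basis.

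**4. Size of the interim difference.** VE at the limit = 1 − 0.6 × exp(−z × 2/√D). Expected Z at 119 events under VE 60% is 3.128 × √0.5 = 2.212.
- Limit 0.00625 (z = 2.4977): VE 62.0%; chance of stopping Φ(2.212 − 2.498) = 39%.
- Limit 0.0015 (z = 2.9626): VE 65.1%; chance of stopping Φ(2.212 − 2.963) = 23%.
- At 120 cases, the first count at which an interim can run, the limits are 0.0064 (t²) and 0.0016 (O'Brien-Fleming type): VE 61.9% and 65.0%, still 39% and 23%.
- At 160 cases the ratio of the two limits has fallen to 1.8.
- Futility at 119 events: VE below about 44% at 0.35022, about 43% at 0.395 to 0.398.

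**5. Size of the final difference.** At 238 events, 0.02275 corresponds to VE 53.7% and 0.025 to VE 53.5%.

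**6. One-sided type I error by pairing.**

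| Interim limit | Final limit | Binding | Non-binding |
|---|---|---|---|
| 0.00625 | 0.02275 | 2.50% | 2.59% |
| 0.00625 | 0.025 | 2.69% | 2.80% |
| O'Brien-Fleming type, 119 cases | 0.025 | 2.45% to 2.48% | 2.55% |
| O'Brien-Fleming type, 180 cases | 0.025 | 2.51% (type II error 0.10) | 2.76% |

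**The case against.** Only one function is actually specified: it is named, coded and written out in both documents. A programmer following the operative text would run O'Brien-Fleming-type spending, so this could be no more than a wrong illustrative table. The t² design is a numerical reconstruction, and the stray word in SAP 14.1.1 may be a drafting slip. The table is labelled an example, no interim runs at 119 cases or fewer, and actual limits depend on the count. Under the operative formula a fixed final 0.025 is close to nominal at half information, and the final conflict moves the VE threshold by only about 0.2 percentage points. Stopping details are also assigned to the DMC charter, and SAP 12.1 requires 95% overall coverage.

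Much of this is fair. The t² design is an inference; 0.00625 would not itself be applied; and the 2.69% to 2.80% arises only if the example's interim value is paired with a final 0.025. None of it removes the contradiction. The example is said to come from the function at exactly half information, and it does not. The 0.10 and the 86.5% remain incompatible at 238 events. SAP 12.1 and 14.1 still disagree on the final level, and SEQDESIGN needs as inputs the very items that conflict. The charter was not available for this check; whatever it says, the protocol and SAP would still need correcting.

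**Conclusion.** The inconsistency is real and should be corrected before any unblinding. The stated rule and the worked example are different designs: the efficacy limit differs about fourfold at half information, and the stated rule with type II error 0.10 needs 260 to 262 events rather than 238. The final level has three descriptions: 0.025, 0.02275, and an unspecified reduced alpha.

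Each coherent design controls the type I error by itself. The fault is that early stopping and the final success threshold are not uniquely fixed by these two documents. The interim consequence is material; the final one is small in VE terms but decisive for a p-value in the gap.

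The event counts, power and VE figures rest on the 4/D variance. Because the documents do not say whether futility is binding, ranges are given. The mismatch in interim alpha spent, 0.0015 against 0.00625, does not depend on either.

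**What to change.** Choose one spending function and one type II error that fits 238 events (0.135, or restate the event target), and state whether futility is binding. Rerun SEQDESIGN. Then align the formula, SAP 14.1.1, both tables, SAP 12.1, the confidence-interval adjustment in the synopsis and Protocol 8.2.1.2, and the final-boundary sentences. Take the final boundary from the chosen design at the actual interim count, not a fixed 0.025.

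Two coherent options:
- Keep the tables. Replace the O'Brien-Fleming text and the 0.10 with t² power-family spending, type II error 0.135 and binding futility.
- Keep O'Brien-Fleming-type spending with type II error 0.135. Reprint the example as 0.0015 / 0.355 / 0.0256 (binding) or 0.0015 / 0.350 / 0.0245 (non-binding).

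The statistical cost is one rerun, two tables and a few sentences. Data collection does not change, and 238 events stand if 0.135 is used. The protocol text goes through the amendment process in Protocol 13.4. The first option is a substantive change to the named function. The second makes early stopping for efficacy less likely than the current example suggests.

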9. SOURCE DOCUMENTATION, STUDY MONITORING AND AUDITING

In order to ensure consistency across sites, study monitoring and auditing will be standardized and performed in accordance with the Sponsor's or delegated contract research organization's (CRO) SOPs and applicable regulatory requirements (e.g., FDA, European Medicines Agency (EMA), and ICH guidelines).

Prior to enrolment of the first study subject, Seqirus or delegate will train investigators and/or their study staff on the study protocol, all applicable study procedures, documentation practices and all electronic systems. CRFs supplied by the Sponsor must be completed for each enroled subject (see [Section 8.3.1, All Enroled Set](#) for definition of enroled subject). Documentation of screened but not enroled subjects must be maintained at the site and made available for review by the site monitor. Data and documents will be checked by the Sponsor and/or monitor.

9.1 Source Documentation

Prior to the start of the study, the site staff participating in the study conduct will be instructed on what documents will be required for review as source documents. The kinds of documents that will serve as source documents will be agreed between Sponsor or delegate and investigator and designees and specified in the SDA prior to subject enrolment.

In addition, source documentation **must** include all of the following: subject identification (on each page), eligibility and participation, proper informed consent procedures, dates of visits, adherence to protocol procedures, adequate reporting and follow-up of adverse events, documentation of prior/concomitant medication/vaccines, study vaccine receipt/dispensing/return records, study vaccine administration information, any data collected by a telephone conversation with the subject and date of completion and reason.

The subject must also allow access to the subject's medical records. Each subject must be informed of this prior to the start of the study and consent for access to medical records may be required in accordance with local regulations.

All safety data reported by subjects must be written down in source documents prior to entry of the data into eCRFs. If there are multiple sources of information (e.g., Subject Diary, verbal report of the subject, telephone contact details, medical chart) supporting the diagnosis of an adverse event, these sources must be identified in the source documents, discrepancies between sources clarified, the ultimate diagnosis must be justified and written in the source documents, and this diagnosis must be captured in the Adverse Event eCRF (AE eCRF). The AE eCRF must also capture which source(s) of

information were used to determine the adverse event (e.g., subject recall, medical chart, Subject Diary).

9.2 Study Monitoring, Auditing and Source Data Verification

Prior to enrolment of the first study subject, Seqirus or its designee (e.g., a CRO) will develop a Clinical Monitoring Plan to specify how centralized and/or on-site monitoring, including clinical specimens reconciliation, will be performed for the study. Study progress will be monitored by Seqirus or its designee as frequently as necessary to ensure:

- that the rights and well-being of human subjects are protected,
- the reported study data are accurate, complete, and verifiable from the source documents and
- the conduct of the study is in compliance with the current approved protocol/amendment(s), GCP and applicable regulatory requirements.

Contact details for the Seqirus team or its designee involved in study monitoring will be provided to the investigator. Study data recorded on eCRFs will be verified by checking the eCRF entries against source documents in order to ensure data completeness and accuracy as required by study protocol.

Data verification may also be performed through a centralized review of data (e.g., checking for outliers or other anomalies). Additional documents such as the investigator site file, pharmacy records, and informed consent documentation must also be available for review if requested. Arrangements for monitoring visits will be made in advance in accordance with the monitoring plan, except in case of emergency.

The investigator and/or site staff must make source documents of subjects enroled in this study available for inspection by Seqirus or its representative at the time of each monitoring visit and Sponsor audits, when applicable. These documents must also be available for inspection, verification and copying, as required by regulations, by officials of the regulatory health authorities (e.g., FDA, EMA and others) and/or ECs/IRBs. The investigator and study site staff must comply with applicable privacy, data protection and medical confidentiality laws for use and disclosure of information related to the study and enroled subjects.

